## **Secondary Outcomes**

### *General*

- immediate and late post-operative morbidity (injury to organs, excess blood loss, blood transfusion, infection (UTI, sepsis, abscess), pain, urinary retention, constipation)
- other adverse effects or complications including mesh erosion or removal
- operating time
- blood loss
- number of nights in hospital
- time until resumption of usual activities

### *Prolapse outcomes*

- subjective recurrence of prolapse
- subjective continuation / recurrence of prolapse symptoms
- objective residual prolapse stage (POP-Q) at original site
- development of new (*de novo*) prolapse at another site
- need for other conservative prolapse treatment (e.g. PFMT, mechanical device)
- need for further surgery for prolapse and/or for urinary incontinence
- time to further surgery
- satisfaction with surgery

#### *Urinary outcomes*

- Urinary incontinence (persistent or *de novo*, and types of incontinence)
- Need for alternative management for incontinence (e.g. PFMT, mechanical devices, pads, surgery, drugs, intermittent catheterisation)

#### *Bowel outcomes*

- Constipation (persistent or *de novo*)
- Bowel urgency (persistent or *de novo*)
- Faecal incontinence (persistent or *de novo*)

#### *Vaginal symptoms and sexual function outcomes*

- Vaginal symptoms

- Dyspareunia / apareunia / difficulty with intercourse (persistent or de novo)

### *Quality of life outcome measures*

- Condition-specific quality of life measures (urinary, bowel, vaginal, sexual)
- General health measure (EQ-5D)

## **Missing data**

### **Loss to follow-up**

Complete loss to follow-up is defined as a participant who has no information on outcomes at any follow-up timepoint, but has not withdrawn consent. Such patients will not contribute data to any of the assessed outcomes.

Partial loss to follow-up is defined as a participant contributing some follow-up data, but no further information is known on other follow-up outcomes. Such participants will contribute to the outcomes for which there are data.

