The surgeons and/or the Recruitment Officers will in conjunction with the British Society of Urogynaecologists (BSUG) Database, complete a Theatre Questionnaire at the time of surgery to ensure a complete record of all surgical techniques and materials used, and any intra-operative difficulties or complications. The Recruitment Officers in each centre will ensure completeness and accuracy of data entry using remote data capture via the study internet based portal at the Study Office in Aberdeen, authored and managed by the UK CRN registered trials unit in Aberdeen (CHaRT). Reciprocal arrangements will be made so that data from PROSPECT study women can be transferred between this and the BSUG database thus reducing duplication of data entry and simplifying the collection of follow up data available to individual gynaecologists via BSUG.

Routine clinical care in hospital

Postoperative care will be standardised as far as possible within each centre and between centres to ensure that differences can be attributed directly to the randomised operative procedures.

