5.1 Questionnaires

Women will be asked to complete a baseline questionnaire before surgery. Follow up questionnaires will be sent by post at 6, 12, 18 and 24 months after surgery. Content will include:

i) Prolapse symptoms (POP-SS,⁷)

- ii) Urinary outcome questions (urinary symptoms and urinary leakage, effect on QOL, http://www.iciq.net/), pad use, catheter use)
- iii) Bowel function outcome questions and effect on QoL
- iv) Sexual function and vaginal symptoms, effect on QoL (http://www.iciq.net)
- v) Health care utilisation questions
- vi) Exercise, weight and height, including pelvic floor exercises
- vii) EQ 5D¹²

and additionally at baseline only:

- i) Obstetric history
- ii) GP address and phone number
- iii) 'Best Contact' at another address for follow up (not wife or partner)
- iv) Other medical problems
- v) Date of operation

Postoperatively within a week of surgery:

- i) infection / pyrexia
- ii) pain and pain relief
- iii) blood transfusion
- iv) vaginal pack
- v) urinary catheter and recatheterisation
- vi) bowel function (need for laxatives)
- vii) complications and return to theatre
- viii) length of stay

At 12 months after surgery (randomised women only):

ii) clinical findings

At 18 months only:

i) Participant Unit Cost Questionnaire

At 6, 12 and 24 months:

- i) Complications
- ii) Need for further treatment for prolapse
- iii) Further treatment for prolapse received or planned, use of health services

Theatre findings and procedures will be recorded in the BSUG database, using a questionnaire designed to be compatible with the requirements of both BSUG and PROSPECT.

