## Outcome Measures

All outcome measures are recorded at baseline, 12 months and 24 months.

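### As worded, the SAP's complete-loss rule removes theatre and in-hospital harms already on record from the between-arm secondary analysis when a woman has no later follow-up data

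*SAP*

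**What the plan says.** SAP 3.1 (Loss to follow-up) has two rules.

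- **Complete loss.** "Complete loss to follow-up is defined as a participant who has no information on outcomes at any follow-up timepoint, but has not withdrawn consent". The consequence is: "Such patients will not contribute data to any of the assessed outcomes".
- **Partial loss.** This covers women who supply some follow-up data. For them: "Such participants will contribute to the outcomes for which there are data".

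SAP 2 (Outcome Measures) gives the schedule as: "All outcome measures are recorded at baseline, 12 months and 24 months". No theatre or in-hospital timepoint is named.

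The secondary outcomes in SAP 2.2 (General) nevertheless include "immediate and late post-operative morbidity (injury to organs, excess blood loss, blood transfusion, infection (UTI, sepsis, abscess), pain, urinary retention, constipation", together with operating time, blood loss and nights in hospital.

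The protocol shows where such data come from. Section 2.4 (Completeness of baseline data collection) describes a Theatre Questionnaire meant to give "a complete record of all surgical techniques and materials used, and any intra-operative difficulties or complications". Section 5.1 has a separate block headed "Postoperatively within a week of surgery", which covers infection, pain, transfusion, catheter use, complications, return to theatre and length of stay.

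SAP 4.1 bases the analysis of both trials on every woman in the arm to which she was randomised.

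**The concern.** Early harms are recorded around the operation, before any questionnaire is posted, so attrition should hardly touch them. The complete-loss rule ties them to attrition all the same. Suppose a woman has a bladder injury or a transfusion on her theatre form, returns no questionnaire and misses the 12-month clinic. As the rule is written, she counts in neither the numerator nor the denominator for that harm.

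Inclusion in an early-harm comparison then depends on something that happens after the harm and may be influenced by it. Safety is part of the principal objective (Protocol 1.2) and of the aim stated in SAP 1. The comparative harm results come from this secondary analysis.

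**Working it through.** The plan states no figure to reproduce here. The point rests on how the passages fit together, with arithmetic only for scale.

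**Step 1. Does the rule reach women who have theatre data?**

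- The trigger is absence of data at follow-up timepoints, a term the SAP does not define.
- Protocol 5.1 uses the term for the postal questionnaires: "Follow up questionnaires will be sent by post at 6, 12, 18 and 24 months after surgery". It lists the post-operative week separately.
- SAP 2 names only baseline, 12 and 24 months. Baseline precedes surgery, so theatre and ward records fall at none of these times.
- Permission to use whatever data exist is given only to women with some follow-up data.
- The exclusion covers every assessed outcome, and SAP 2.2 makes early harms assessed outcomes.
- The SAP defines no safety population, no exemption for peri-operative outcomes and no rule for death.

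Read together, these exclude a woman with theatre and ward records but nothing later, contrary to SAP 4.1. SAP 3.2 applies the same loss rules to women who withdraw.

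**Step 2. What is not affected?**

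- POP-SS at 12 months: a completely lost woman has no 12-month score, so the rule changes nothing there.
- Safety recording: Protocol 8.4.2 sends listed occurrences, including organ injury and death, to the Data Monitoring Committee. Protocol 8.4.3 puts all deaths on SAE forms.

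**Step 3. How many women?**

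Randomised: 1353 + 155 = 1508 (Protocol Appendix IV; the cells of SAP Tables 2 and 3 give the same sums).

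Complete loss requires no data at every timepoint, so its share cannot exceed the share missing at any single one. If the planned 15% one-year dropout holds, 15% is a ceiling. If the pilot's 94% response at 6 months carried over, the ceiling would be 6%, or 1508 x 0.06 = 90 women. The actual share is not given, so 1% to 15% is assumed.

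| Assumed complete loss | Primary (1353) | Secondary (155) | Both (1508) |
|---|---|---|---|
| 1% | 14 | 2 | 15 |
| 5% | 68 | 8 | 75 |
| 15% | 203 | 23 | 226 |

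**Step 4. What could it do to a reported rate?**

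Let h be the true early-harm rate, c the complete-loss share, and r the harm rate in lost women divided by that in retained women. Since h = (1 - c) x hk + c x r x hk, the analysed rate is hk = h / (1 - c + r x c).

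Take h = 2.8%, the organ-damage rate for blind introducer devices in Protocol Appendix I, section 1.3. It serves only as a scale and is not a rate for the primary trial. The values of r are assumptions with no source in the documents.

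| c | r = 1 | r = 2 | r = 3 |
|---|---|---|---|
| 1% | 2.80% | 2.77% | 2.75% |
| 5% | 2.80% | 2.67% | 2.55% |
| 15% | 2.80% | 2.43% | 2.15% |

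At r = 1 the rate is unchanged and only information is lost: in the primary trial about 0.4, 1.9 and 5.7 harmed women at 1%, 5% and 15% loss (for example 1353 x 0.05 x 0.028 = 1.9).

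If c and r are the same in two arms, both rates shrink by the same factor and their ratio is unchanged. Distortion of the relative comparison needs c or r to differ by arm.

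The mesh kit was allocated to 44 + 3 = 47 women (SAP Table 3). At 2.8% that is 47 x 0.028 = 1.3 expected injuries, so one dropped event would matter to what is reported, although an exclusion of even one is not certain.

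**The case against.** The strongest reply is that the rule need not be read this way. Protocol 5 dates follow-up from the operation, and Protocol 6.2 places assessment in hospital after surgery beside the later questionnaires. On that reading, a woman with ward records has follow-up information and is a partial loss, so her data are used. The schedule sentence in SAP 2 is also plainly loose: it omits the 6-month point that SAP 4.2 models, and it cannot literally apply to operating time.

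This reading is possible and may be what was intended. The SAP does not state it, however, and Protocol 5.1 and SAP 2 point the other way. Two analysts could derive different denominators for the same harm, which is reason enough to settle the wording.

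The reply succeeds against stronger inferences that a reader might draw:

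- **That harms or deaths vanish from safety oversight.** They do not; Protocol 8.4.2 and 8.4.3 keep separate routes. Mortality is also not a named SAP outcome. A death could enter only under other adverse effects or complications.
- **That 6% to 15% of women would be dropped.** Those figures are pilot non-response at one timepoint and planned one-year dropout. They are ceilings for complete loss, not a range for it. Tracing through GPs and nominated contacts (Protocol 4.2) is intended to limit loss.
- **That harm rates are shown to be understated, or the arm comparison biased.** Both need loss to be related to harm, and distortion of the relative comparison needs that pattern to differ by arm. The documents show neither.

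**Conclusion.** The point holds as a should-fix on the secondary safety outcomes. On its plain wording, the complete-loss rule discards early harms already on record and makes their analysis depend on later follow-up, against the SAP's own as-randomised principle.

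Its size cannot be established from the documents. About 15 to 226 of 1508 women would be affected under an assumed 1% to 15% complete loss, and the true number may lie well towards the low end. The cost is lost information if loss is unrelated to harm; understatement arises only if harmed women are lost more often. The finding is limited to the between-arm secondary analysis.

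**What to change.** Four wording changes to the SAP:

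1. In SAP 3.1, limit the exclusion to outcomes for which the woman has no data.
2. Add that theatre, in-hospital and NHS-record outcomes are analysed in all randomised women with such records, in the arm to which they were randomised. Make SAP 3.2 consistent with this, within the consent given.
3. State that deaths before the first follow-up are reported by arm under adverse effects or complications, and are not classed as loss to follow-up.
4. In SAP 2, replace the schedule sentence with the actual timepoints, adding theatre, in-hospital and 6 months to those already named.

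It would also help to report, by arm, how many women have early records but no later data, since that settles the size of the issue.

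The cost is drafting time. The theatre and post-operative forms and the NHS-record check (Protocol 5.2) are already in the protocol, so no new data collection is needed.

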### **Withdrawals**

If a participant prospectively withdraws consent, no further data are captured or retained on or after the date of withdrawal of consent. Depending on when the consent is withdrawn, the above rules on loss to follow-up apply.

### **Post-randomisation exclusions**

If a participant is excluded from the trial, then their data will be excluded from analyses and will not contribute to any of the assessed outcomes.

### **Imputation**

Imputation of missing baseline data (collected prior to randomisation) will be undertaken in order to reduce bias. Although no imputation of missing participant-level outcome data will be carried out in the main analysis of the primary outcome, imputation of instruments (e.g. POP-SS) will be undertaken at item-level according to the rules of the specific instrument.

## **Sensitivity analyses**

It is recommended that sensitivity analyses are carried out where there are missing outcome data. For the primary outcome POP-SS at data 12 months we will explore the impact of missing data on the complete-case treatment estimates and confidence intervals by using multiple imputation and pattern mixture modelling methods depending on level and patterns of missing data.

## **Statistical Methods**

### **General Methods**

The statistical analysis of the RCTs will be based on all women as randomised, irrespective of subsequent compliance with the treatment allocated (intention to treat). The principal comparisons will be:

- In women having a primary prolapse repair,
  - a standard anterior and/or posterior repair will be compared with a standard repair using a biological graft inlay; and
  - a standard anterior and/or posterior repair will be compared with a standard repair using a non-absorbable or combined mesh inlay.
- In women having a secondary prolapse repair,
  - a standard anterior and/or posterior repair will be compared with a standard repair using a non-absorbable or combined mesh inlay; and
  - a standard anterior and/or posterior repair will be compared with a mesh kit procedure using an introducer device.

The two trials are being considered independently because different surgical options are considered to be appropriate for clinical reasons. Women who are not randomised but who are in the Comprehensive Cohort group will be analysed according to the operation actually carried out.

Descriptive statistics will be tabulated by treatment allocation for all outcomes (mean and SD for continuous data, proportions for binary data). Treatment effects will be estimated with 95% confidence intervals for all outcomes (mean differences for continuous data, odds ratios for binary data). Statistical significance will be at the 5% level and corresponding confidence intervals will be derived. Analyses will be conducted using SAS v9.3.

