6.3 Statistical analysis

A single principal analysis is anticipated at 12 months after the last woman is recruited. The Data Monitoring Committee will determine the frequency of confidential interim analyses, but at present these are planned on four occasions during the data collection period.

All analyses within the RCT will be based on the intention-to-treat principle. All outcomes in both trials will be described with the appropriate descriptive statistics where relevant: mean and standard deviation for continuous and count outcomes, or medians and inter-quartile range if required for skewed data, numbers and

percentages for dichotomous and categorical outcomes (for example subjective recurrence of prolapse).

Analysis of the primary outcome (POP-SS) will estimate the mean differences (and 95% confidence interval) between the intervention and control groups using a general linear model that adjusts for the minimisation covariates and other important prognostic covariates, including the baseline symptom score, at 12 months after surgery. A similar analysis will be used to analyse the primary outcome at 6 and 24 months.

All secondary analyses will be analysed in a similar manner but using the appropriate generalised linear model (for example logistic regression for dichotomous data such as subjective prolapse failure, Poisson or negative binomial regression for count data such as number of nights in hospital) or time to event methods (e.g. Cox regression on time to further surgery) where required. We will explore analysing outcomes at all time points simultaneously using for example, Generalised Estimating Equations or Generalised Linear Latent and Mixed Models, and relevant link functions, to explore changes in outcome over time.

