1.2.2 Surgical management for women with anterior or posterior vaginal wall prolapse

A new update of the Cochrane Review of surgery for prolapse¹ identified 13 RCTs of surgical interventions for women with anterior or posterior pelvic organ prolapse. The IP review⁴ for NICE has identified a further nine RCTs which are not yet included in the Cochrane review. The total number of women receiving mesh in the IP systematic review⁴ was 4569: mesh was inserted using an introducer device, trochar or kit in 503 of these women. There were no data on the differential effects in women having primary as opposed to secondary surgery: all the trials reported both groups of women together despite their potentially different prognoses.

Differences in inclusion criteria or interventions (e.g. types of women, operations or mesh) precluded much useful meta-analysis or reliable conclusions. There were two small but inconclusive RCTs comparing standard repairs with or without mesh with site specific fascial defect repairs^{22;23}. There were another two small and inconclusive RCTs which included a mesh introducer device arm. ^{24;25}

For anterior vaginal wall prolapse, the limited RCT data from the Cochrane review¹ and the IP review⁴ (9 RCTs) suggested that any mesh might reduce subsequent objective anatomical relapse (77/557, 14% relapse) compared with using no mesh (179/591, 30%) (RR 0.48, 95% CI 0.32 to 0.72) in the short term. The IP review⁴ also included additional data from non-randomised comparative studies and case series. Using these extra data, non-absorbable synthetic mesh had the lowest failure rate:

- compared with absorbable synthetic mesh (OR adjusted for bias from study design 0.23, 95% CI 0.12 to 0.44);⁴ and
- compared with absorbable biological mesh (OR adjusted for bias from study design 0.37, 95% CI 0.23 to 0.59).⁴

On the other hand, the mesh erosion rates increased from 1% (95% CI 0.1% to 4%) with synthetic absorbable mesh to 6% with absorbable biological mesh to 10% with non-absorbable synthetic mesh.⁴ The data were too sparse, however, for other

reliable statistical analysis. There were insufficient data on women's subjective prolapse symptoms or complications such as infection, blood loss or dyspareunia, and none on long term outcomes. Particular safety worries are related to the use of introducer devices (trochars) that are needed for the blind insertion of mesh into intra-pelvic spaces.²⁶

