**Table 3: Number of participants randomised to each stratum in the secondary RCT**

Stratum	Standard repair (A)	Synthetic mesh (B)	Mesh kit (C)
RCT2	24	24	44
RCT2B	31	28	n/a
RCT2D	1	n/a	3

In the primary RCT, RCT1 will be analysed on its own and treatment effects for treatments B and C (compared with A) will be estimated. In addition, the RCT1 and RCT1B strata will be combined (using just data in arms A and B) in a separate model to create a further estimate of the treatment effect between A and B. Similarly, the RCT1 and RCT1C strata will be combined (using just data in arms A and C) in a separate model to create a further estimate of the treatment effect between A and C. Where strata are combined, the stratum variable will be fitted as a fixed effect in the model. The secondary trial will be similarly analysed, although RCT2 will not be combined with RCT2D due to the small number randomised to RCT2D.

Secondary outcomes will be analysed in a similar fashion to the primary outcome using appropriate link functions.

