### **Non-compliance will allocated treatment**

The primary analysis strategy of the trial will follow the intention-to-treat principle, i.e. participants will analysed as randomised, regardless of the intervention received. However, secondary analyses may be undertaken to investigate issues relating to compliance (e.g. mesh inlays being misidentified as mesh kits). Depending on levels and patterns of non-compliance analyses methods other than intention-to-treat may be used, for example per-protocol analyses or estimation of complier average treatment effects.

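### Mesh erosion or removal falls under the SAP's by-allocation odds-ratio rule, which gives an inestimable or unstable ratio against a no-mesh reference, and no rate among women who received mesh is fixed

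*SAP*

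**What the plan says.** The SAP lists, among its general secondary outcomes, "other adverse effects or complications including mesh erosion or removal". Its General Methods section then sets three rules with no exception:

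- The analysis of the trials "will be based on all women as randomised, irrespective of subsequent compliance with the treatment allocated (intention to treat").
- "Descriptive statistics will be tabulated by treatment allocation for all outcomes".
- "Treatment effects will be estimated with 95% confidence intervals for all outcomes (mean differences for continuous data, odds ratios for binary data").

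The text after SAP Table 3 adds: "Secondary outcomes will be analysed in a similar fashion to the primary outcome using appropriate link functions". Protocol section 6.3 gives as an example "logistic regression for dichotomous data such as subjective prolapse failure". Protocol section 3.1 makes standard repair, which uses no mesh, the reference for every comparison.

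On departures from allocation, the SAP says: "Depending on levels and patterns of non-compliance analyses methods other than intention-to-treat may be used". It does not tie this to any outcome. Analysis by the operation actually performed is fixed only for the non-randomised cohort.

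**The concern.** A woman with no mesh in her body cannot have mesh erosion or mesh removal. The reference arm's event count for this component is therefore zero, or a small number that depends on mesh from some source other than her allocated repair. An odds ratio against such an arm is either undefined or reflects how much incidental mesh was present, and says little about the mesh under test.

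The by-allocation rate has a second limitation. Women allocated to mesh who did not receive it stay in the denominator, although the allocated mesh cannot harm them. Protocol Appendix IV makes provision for recruited women who never had a prolapse operation within the trial, so some non-receipt is foreseen.

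Protocol section 1.2 includes safety in the principal objectives. Women and commissioners need to know the absolute risk once mesh is placed, and the SAP does not commit to reporting it for randomised women.

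**Working it through.** The documents give no expected rate, odds ratio or precision for erosion as a trial outcome, so there is no planned figure to reproduce. The check puts the protocol's background rates into the SAP's arm sizes.

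**Inputs**
- Arm sizes (SAP Table 2, strata pooled as the SAP prescribes): standard v synthetic 253+178 = 431 v 256+181 = 437; standard v biological 253+116 = 369 v 255+114 = 369.
- Erosion rates (Protocol Appendix I, 1.2.2): from synthetic absorbable "mesh to 6% with absorbable biological mesh to 10% with non-absorbable synthetic mesh". These come from a review paragraph on anterior prolapse with no time frame. Applying them to all repairs with no loss to follow-up is an assumption.
- Expected mesh-arm events: 0.10 × 437 ≈ 44; 0.06 × 369 ≈ 22.

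**No standard-arm events.** The odds ratio is (44 × 431)/(393 × 0), which is infinite; the exact conditional 95% CI is 12.4 to infinity. For biological mesh, 22/369 v 0/369 is also infinite, with exact CI 5.8 to infinity. An unpenalised logistic fit to the synthetic table does not converge (standard error about 23,000). Covariate adjustment does not remove the zero cell.

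**A few standard-arm events.** With c events among n standard-arm women, and a events among m mesh-arm women, OR = a(n − c)/[(m − a)c], with a Woolf interval. The risk difference is a/m − c/n.

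| Standard-arm events | Synthetic OR (95% CI) | Synthetic risk difference, points | Biological OR (95% CI) |
|---|---|---|---|
| 1 | 48.1 (6.6–351) | 9.8 | 23.3 (3.1–174) |
| 2 | 24.0 (5.8–99.7) | 9.6 | 11.6 (2.7–49.8) |
| 3 | 16.0 (4.9–51.9) | 9.4 | 7.7 (2.3–26.1) |
| 5 | 9.5 (3.7–24.3) | 8.9 | 4.6 (1.7–12.3) |

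Four more events cut the synthetic odds ratio fivefold and move the risk difference by less than one point.

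**Is one to five plausible?** There are two routes in the primary trial:
- *Continence tape.* The SAP expects 15% to have a concomitant continence procedure: 0.15 × 431 ≈ 65 women. If all had tape, an assumed 1–4% erosion rate gives 0.6–2.6 events.
- *Crossover.* An assumed 1–5% of 431 women given synthetic mesh, at 10% erosion, gives 0.4–2.2 events.

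The two routes are of similar size and together reach at most about 4.8.

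**Dilution.** By-allocation rate = rate in recipients × share receiving mesh, if few women gain mesh otherwise. For assumed receipt of 90%, 80% or 70%:
- synthetic: 39, 35 or 31 of 437 = 8.9%, 8.0% or 7.1%, against 10%;
- biological: 20, 18 or 15 of 369 = 5.4%, 4.9% or 4.1%, against 6%.

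**Secondary trial (SAP Table 3).** At an assumed 10%, expected events are 2.4 of 24 (synthetic, RCT2), 5.2 of 52 (RCT2 with RCT2B) and 4.4 of 44 (kit). The chance of no events among 24 is 0.9^24 ≈ 8%, so a mesh arm may be empty too.

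**The case against.** The case for leaving the SAP alone has four parts.

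- *The listed outcome is wider than erosion.* Most complications can occur in any arm (Protocol 8.4.2), and an intention-to-treat comparison of them is meaningful. This stands, and that comparison should stay. It does not help the erosion component if that is reported separately.
- *Proportions by allocation are already planned,* so a 44/437 v 0/431 split would be visible. This also stands, but the denominator is women allocated, not women with mesh.
- *The SAP does not mandate unpenalised logistic regression.* It speaks of suitable link functions, and the protocol's logistic model is an example. A reader might infer that no usable interval exists with a zero cell; that is wrong, because the exact lower limits of 12.4 and 5.8 are informative. However, the SAP names no method for sparse cells.
- *Receipt-based analysis is partly provided for.* Per-protocol or complier-average methods may be used, and Protocol 3.1 requires mesh type and divergence to be documented. Protocol 6.2 also cites Dummy Tabulations that are in neither document, so a table by mesh received may exist there. What remains is that the SAP text makes such analysis optional and does not link it to mesh events.

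A reader might also infer that all standard-arm women, 547 of 1353 (40%) and 56 of 155 (36%), cannot have the event by design, so that any such event signals a protocol deviation. The documents do not support this. Protocol 2.3 allows a concomitant incontinence procedure such as TVT. In the secondary trial it also leaves a concomitant de novo repair to clinical choice, outside the allocation. Both routes can put mesh in a standard-arm woman within protocol.

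**Conclusion.** The concern holds for mesh-specific events. As written, the rule gives no finite odds ratio with no standard-arm events. With one to five events, it gives a synthetic ratio anywhere from about 48 down to 9.5. These figures rest on the protocol's background rates and full arm sizes; the instability follows from the near-empty reference cell and does not depend on the exact rates.

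The understatement of risk is conditional. A reader might take it as established, but the documents give no non-receipt rate, and Protocol 2.4 expects low non-compliance among gynaecologists. Under the assumed 10–30% non-receipt, 10% is reported as about 9–7%. For scale, the 95% interval for 44/437 is 7.6% to 13.2% (Wilson), so the shift is modest beside sampling error unless non-receipt is high, although it is systematic.

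This concerns one component of a secondary safety outcome. It does not touch the primary analysis or the sample size, and it is no argument against intention-to-treat for complications in general.

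**What to change.** Amend SAP General Methods and the secondary-outcome text after Table 3:

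1. Keep by-allocation counts for all outcomes, and the intention-to-treat comparison for complications that any woman can have.
2. For mesh-specific events (erosion or exposure, removal or revision), add counts and absolute risks with exact 95% CIs among women in whom mesh was placed. Break these down by mesh class and by source: randomised repair, concomitant repair or continence tape. Show randomised and cohort women separately and label the table descriptive.
3. If a between-arm contrast is given for these events, use a risk difference or an exact or penalised method in place of the ordinary odds ratio.

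The cost is some wording and one extra table. Materials used are already recorded on the Theatre Questionnaire (Protocol 2.4), and mesh type and divergence under Protocol 3.1. The limitation to state is that rates among recipients are not a randomised comparison, which is why the table supplements the by-allocation analysis and does not replace it.
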